#### Logistical Possibilities

Originally, impulse generators for deep brain stimulation electrodes accommodated only single quadric-polar brain electrodes. Consequently, deep brain stimulation was necessarily constrained by the lack of pulse generator flexibility. Currently available impulse generators readily accept multiple brain electrodes. Therefore, it is logically possible to consider utilizing multiple brain electrodes simultaneously. The studies suggested would require at least two electrodes to be placed in one cerebral hemisphere (one for motor improvement and one for potential cognitive implications). Trials would need to include designs to determine the impact of DBS in targets considered singly (e.g. STN or fornix/hypothalamus) and in combination (e.g. STN and fornix/hypothalamus).

I propose controlled studies implanting PD patients who are otherwise undergoing unilateral DBS-GPi or DBS-STN with a unilateral DBS electrode with stimulation to the

fornix/hypothalamus region, i.e. tandem DBS. Such patients would receive a single IPG, as would otherwise be required for such surgery. Patients subsequently undergoing second-sided surgery for motor parkinsonism would concurrently also receive a second electrode with stimulation for the fornix/hypothalamus. Stimulation to the fornix/hypothalamus would be accomplished with either the same rate/frequency as for the unilateral basal ganglia structure or utilize 3.0-3.5 V with a frequency of 130 Hz and pulse width of 90 microseconds.

Neuropsychological studies and dementia status immediately prior to and years post-operatively would form the primary outcome measure for these tandem DBS studies. Historical results, with single hemispheric electrodes (either unilateral or bilateral) could serve as potential comparative data for secondary analyses.

MRI scans will be completed for serial hippocampal volume measures. Scans will be evaluated by [name].

Pathological studies of brain from patients at death would subsequently help to determine the nature of results, including ability to ascertain whether neurogenesis or other mechanism might be associated with fornix/hypothalamus-DBS/tandem DBS.

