#### Assessment and Statistical Analyses

The primary method of assessing treatment effects will be paired t-tests at the various post-operative intervals.

The primary efficacy parameters are neuropsychological battery scores over time in comparison with pre-operative scoring.

Secondary efficacy parameters will include UPDRS scoring (motor and activity of daily living subscores).

The primary endpoints will be the change in neuropsychological scoring from baseline to 12 and 36 months, expressed as a percentage change from baseline (employing “on”/“on” post-operative status versus “on” pre-operative values. Two-sided two-sample t-tests will compare post-operative changes to pre-operative data. Such

comparisons will take place when the full contingent of patients are accrued and have completed such assessments.

The effect of stimulation on cognitive functioning and mood state will be assessed using t-tests for dependent samples to compare performance on neuropsychological tests and POMS scores in the “on” and “off” condition at each follow-up evaluation. Changes in cognitive functioning, mood, and HRQOL from presurgical baseline will be analyzed using repeated-measures ANOVAs, with neuropsychological test scores as the DV and time of testing as the repeated measure. Demographic variables and measures of social support and locus of control will be entered into analyses of covariance whenever appropriate.

Hierarchical multiple regression analyses will be used to determine the relationship between presurgical psychosocial and neuropsychological variables and postsurgical outcome, as measured by HRQOL.

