### **Basic study plan**

This is a prospective study of Parkinson's disease outcome following a deep brain stimulation procedure. Twelve Parkinson's disease patients, with significant disability despite optimal medical therapy, will undergo stereotactic placement of unilateral deep brain stimulation electrodes (Medtronic 3387 electrode) into the subthalamic nucleus or GPi AND the hypothalamus/fornix during a single surgical procedure (Tandem DBS). A single, dual implantable pulse generator will be placed to control both DBS leads. Patients will be evaluated pre- and post-operatively (at, 3, 12, , 24months 36-months (and yearly thereafter) with quantitative outcome measures. The study will include measures of motor function, speech, neurobehavior, socioeconomic impact and quality of life.

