### **Scientific basis or justification**

Parkinson's disease is a common neurodegenerative disorder with no treatment that definitively alters the natural progression of the condition. With progression of symptoms, patients with Parkinson's disease (PD) frequently develop significant disability despite optimal medical therapy. This study is designed to test a new technology for the treatment of severe PD.

Currently available surgical treatments, such as pallidotomy, GPi-DBS, and STN-DBS, offer some benefit for selected patients but do not influence cognitive dysfunction. Reports concerning cognitive benefit have documented potential improvement with

placement of DBS electrodes and stimulation in the fornix/hypothalamus in normal and patients with mild Alzheimer's disease.

We propose a pilot study of tandem DBS in 12 PD patients experiencing disability despite optimal medical therapy. The subthalamic nucleus and substantia nigra reticulata are crucial output nuclei in the cortico-basal ganglia-thalamic anatomy in which abnormal physiological activity have been described in animal models of parkinsonism and confirmed in human PD. DBS of STN bilaterally has been shown to ameliorate parkinsonism in both settings. The substantia nigra reticulata is an output nucleus that shares neurophysiological function with the internal segment of the globus pallidus or medial pallidum. Lesioning or DBS of the medial pallidum have both been shown to improve parkinsonism in animal models and human parkinsonism. We believe that DBS of both STN and hypothalamus would prove optimal in terms of reducing both parkinsonian and cognitive signs and symptoms.

Our surgical technique (MRI-microelectrode-guided procedure) allows for the implantation of bihemispheric DBS leads and pulse generator within the space of 3 hours.

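### The primary endpoints of a single-group, before-and-after study are assigned a two-sample t-test, in conflict with the paired t-tests that the plan names as its primary method

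*Combined protocol and SAP*

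**What the plan says.** Assessment and Statistical Analyses opens with "The primary method of assessing treatment effects will be paired t-tests at the various post-operative intervals". The section Statistical method/rationale, in the summary for the review board, carries the same sentence and mentions no other test.

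Assessment and Statistical Analyses then says "The primary efficacy parameters are neuropsychological battery scores over time in comparison with pre-operative scoring" and defines the endpoints: "The primary endpoints will be the change in neuropsychological scoring from baseline to 12 and 36 months, expressed as a percentage change from baseline". The next sentence assigns the test: "Two-sided two-sample t-tests will compare post-operative changes to pre-operative data".

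The following paragraph turns to stimulation on versus off. That effect "will be assessed using t-tests for dependent samples to compare performance on neuropsychological tests and POMS scores". The same paragraph assigns repeated-measures ANOVA to change in cognitive functioning, mood and quality of life from the presurgical baseline.

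On design, Scientific basis or justification says "We propose a pilot study of tandem DBS in 12 PD patients experiencing disability despite optimal medical therapy", and Basic study plan says that the twelve patients "will undergo stereotactic placement of unilateral deep brain stimulation electrodes", at both targets in one procedure. No concurrent comparison group is described. The only outside data are historical single-electrode results, which according to Logistical Possibilities "could serve as potential comparative data for secondary analyses".

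**The concern.** A two-sample t-test assumes two independent sets of observations. Here the pre- and post-operative scores come from the same 12 people. Moreover, the endpoint is a percentage change from baseline, and no pre-operative percentage change exists to serve as a second sample. The sentence therefore cannot be carried out validly for this design.

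Three things are at stake.

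- **Lost sensitivity.** If the test is run on raw scores, it discards the within-patient correlation, so a real cognitive benefit or a real cognitive decline could be missed.
- **Wrong level in the other direction.** If percentage change is set against a column of zeros, the test claims twice the degrees of freedom that the data supply.
- **Two tests, both in the plan.** Either could be reported as pre-specified, and the plan does not prevent that choice from being made after the results are known.

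**Working it through.** The plan gives no sample-size calculation, alpha, SD, correlation or effect size, so it has no figure of its own to reproduce.

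**Inputs from the documents.** n = 12 in one group; two-sided test; each patient measured before and after surgery.

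**Assumptions.** 5% level; normal scores with equal SD σ before and after; pre/post correlation ρ from 0 to 0.8; no dropout; illustrative true changes of 0.5, 0.8 and 1.0 SD.

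**Step 1: is there a reading with a second sample?** The sentence names pre-operative data as its comparator, so it does not refer to an outside group. Historical results are offered only for secondary analyses. The plan uses the term for dependent samples elsewhere in the same section, so it distinguishes the two kinds of test. No such reading is left.

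**Step 2: two-sample test on raw scores.**

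- Standard error used by the two-sample test: σ√(2/n).
- Actual standard error of the mean change: σ√(2(1−ρ)/n).
- Ratio: 1/√(1−ρ), which is 1.41, 1.83 and 2.24 at ρ = 0.5, 0.7 and 0.8.
- Critical values: 2.074 (22 df, two-sample) and 2.201 (11 df, paired).
- Nominal 95% CI half-width at SD = σ, two-sample: 2.074 × √(2/12) = 0.85 SD.
- The same, paired: 2.201 × √(2(1−ρ)/12) = 0.64, 0.49 and 0.40 SD at ρ = 0.5, 0.7 and 0.8.

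Type I error and power come from simulation of bivariate normal data. Paired power was checked against the noncentral t.

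| ρ | Type I error, two-sample | Power at 0.5 SD, two-sample / paired | Power at 0.8 SD, two-sample / paired |
|---|---|---|---|
| 0 | 5.0% | 22% / 20% | 47% / 43% |
| 0.3 | 2.2% | 18% / 27% | 46% / 57% |
| 0.5 | 0.9% | 15% / 35% | 46% / 71% |
| 0.7 | 0.16% | 11% / 53% | 46% / 90% |
| 0.8 | 0.04% | 8% / 70% | 45% / 98% |

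The paired test holds its 5% level at every ρ. For a 1.0 SD change, two-sample power is about 70% at ρ = 0.5 and 76% at ρ = 0.8, against 88% and 99.9% paired. The fall in two-sample power as ρ rises is thus a feature of the smaller effect. The paired test is ahead at each of these effects once ρ is 0.3 or more.

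**Step 3: percentage change against a column of zeros.** Let s be the SD of the percentage changes. The pooled variance is (s² + 0)/2, so the standard error is √((s²/2)(2/n)) = s/√n. The statistic equals the one-sample t, which has 11 df, but it is referred to 22 df. The real level is 2 × P(t₁₁ > 2.074) = 6.2% if the percentage changes are normal.

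**Step 4: overlap with the ANOVA.** The repeated-measures ANOVA covers change in cognitive functioning from the presurgical baseline, which is also the subject of the primary endpoints. It respects the within-patient structure and is not labelled primary, but its rank relative to the t-tests is not stated.

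**The case against.** The best defence is that this is a drafting slip with an obvious default. Paired t-tests are named as the primary method in two sections, and a competent analyst would pair the data. It is also a 12-patient pilot with no stated alpha, power or decision rule. The slip is quite possible, but the plan does not compel the default: the two-sample sentence is the one that directly follows the endpoint definition. The plan also sets out formal tests, and with 12 patients the choice between them can change the result.

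It is fair to say that the power figures rest on assumed inputs. The size of the loss depends on the effect and the correlation, and at ρ = 0 the two tests nearly coincide. The 6.2% level in the other reading is a mild inflation.

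Three stronger inferences should be resisted.

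- **Percentage change against raw baseline scores.** A reader might take the sentence literally and infer that the sponsor means to compare these two quantities, with near-certain false positives on some scales. No analyst would plausibly do this, and the documents give no scale from which to compute a rate.
- **Upward bias.** A reader might infer that mean percentage change is always biased upward. That depends on the model. It can be non-zero with no true change, for example through regression to the mean, but if the post-operative score is the baseline times an independent factor with mean 1, it is zero.
- **Raw scores required.** A reader might infer that the primary endpoint has to move to raw scores. The endpoint sentence specifies percentage change, and a valid within-patient test of it exists.

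**Conclusion.** The point stands, and the plan should be corrected before analysis. The contradiction rests on the text and the single-group design alone and needs no calculation. The test assigned to the primary endpoints is not valid for one group compared with its own baseline.

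The direction of the error depends on how the sentence is carried out: strongly conservative on raw scores at the correlations of 0.5 to 0.8 considered here, mildly anti-conservative on percentage change against zeros. The sizes are conditional on normality and a 5% level and, for the raw-score figures, also on equal SDs and the correlations and effects shown. They illustrate the consequence and do not estimate what will happen in this trial.

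**What to change.** In Assessment and Statistical Analyses, replace the two-sample sentence with a within-patient test. Suggested text: *At 12 and at 36 months, each patient's score will be compared with the same patient's pre-operative score by a two-sided paired t-test.* This matches the method already named at the start of that section and in Statistical method/rationale.

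If the sponsor keeps percentage change as the tested quantity, as the endpoint sentence implies, name the corresponding test: a two-sided one-sample t-test of percentage change against zero with n−1 df (11 if all 12 are assessed). Note beside it that the mean percentage change can differ from zero without a true change and that it is undefined for a zero baseline. Add a clause to Statistical method/rationale so that the two sections agree.

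In either case, state which scale is tested, and state that the repeated-measures ANOVA of change from presurgical baseline is supportive, so that one type of primary test remains.

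The cost is small: a few sentences of wording and one decision by the sponsor, raw score or percentage change. That decision is more than editorial, because choosing raw scores changes the tested quantity. No data or visits are added. The change settles the type of test only; it does not address multiplicity across two time points and a battery of scores.

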#### Dementia and Parkinson's disease

Dementia in Parkinson's disease (PD) represents the most frequent, eventually disabling feature of this common neurodegenerative disorder. It also is a strong predictor of survival [5].

Parkinson dementia/dementia with Lewy bodies represents the second most common form of disabling dementia. Characteristics of dementia in parkinsonism include progressive dementia with deficits in attention and executive function [6]. Recurrent, complex visual hallucinations frequently occur and may be accompanied by REM sleep behavior disorder (concurrently or prior to development of other features). Additionally, many patients experience pronounced variability in cognition with profound fluctuations/variability in attention and alertness. Fluctuations in cognitive functioning and deficits in attention and executive function, often without prominent memory impairment, is a core feature of dementia with Lewy bodies [6], and occurs particularly in early stages. Such variability is a hallmark of dementia with Lewy bodies that differentiates this form of cognitive decline from Alzheimer's disease and aging [7].

Unfortunately, the two most common disabling clinical features of PD, namely postural instability leading to falls and dementia have evaded effective treatment. Additionally, these features are increasingly common in aging PD patients, precisely the demographic who are avoided by most centers performing DBS surgery.

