A subsequent trial has ensued examining the impact of DBS on memory circuits in Alzheimer’s disease (AD) [11]. This trial recruited six patients with early AD. All had Clinical Dementia Rating scores of 0.5 or 1.0 [12] and scores between 15-26 on the Mini Mental State Examination (MMSE)[13]. Each were implanted bilaterally in the vertical portion of the fornix within the hypothalamus. Assessments with the Alzheimer’s Disease Assessment Scale, Cognitive Subscale (ADAS-Cog)[14] took place at baseline and 6 and 12-months post-operatively. After 6 months of stimulation, 4 of 6 patients showed improvement, with lowering of 1.3-4.0 points in the ADAS-Cog scores. This magnitude compares favorably to the reported impact of donepezil in mild cognitive impairment, which is 0.5 points [15].

After 12 months, one patient had 4.4 points lower than baseline, 2 patients a 2-point increase, 1 patient a 5-point increase, and 2 patients >5 point increases. The expected change in the cohort of 6 was: 2 patients had less than expected increases, 1 more, and 3 within the expected range. Interestingly the patient with the greatest improvement experienced the most vivid experiential experience with stimulation during surgery, as had been the case with the original anectodal patient reported. Functional imaging carried out in this trial also suggested that fornix/hypothalamic-DBS produced changes in the

cognitive and limbic brain areas (improved glucose metabolism), were the basis for observed changes in some of the AD patients. These authors also suggest that DBS may drive greater delivery of neurotrophin brain-derived neurotrophic factor and influence neurogenesis in the diseased hippocampus.

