### Summary

DBS utilizing “traditional motor targets” for PD patients has provided improvement in functional “on” time and reduced tremor compared to standard medical therapy. However, subsequent risk for cognitive decline/dementia remains and development of these features leads to early disability and death. Potential improvements in cognitive function and neurogenesis are conceivable with tandem DBS targeting STN/GPi and the fornix/hypothalamus and should now be considered for systematic study in PD.

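### With 12 patients and no provision for missed tests, a categorical-visit mixed model should replace the repeated-measures ANOVA and accompany the primary paired t-tests as a sensitivity analysis; the HRQOL regression should be exploratory

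*Combined protocol and SAP*

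**What the plan says.** The protocol's Assessment and Statistical Analyses section layers several analyses on the same scores:

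- Main method: "The primary method of assessing treatment effects will be paired t-tests at the various post-operative intervals". The section later also calls the tests two-sample. I use the paired reading, which the Statistical method/rationale section repeats.
- Time points: "The primary endpoints will be the change in neuropsychological scoring from baseline to 12 and 36 months", expressed as a percentage of baseline.
- Longitudinal analysis: "Changes in cognitive functioning, mood, and HRQOL from presurgical baseline will be analyzed using repeated-measures ANOVAs", with time of testing as the repeated measure.
- Quality of life: "Hierarchical multiple regression analyses will be used to determine the relationship between presurgical psychosocial and neuropsychological variables and postsurgical outcome, as measured by HRQOL".

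Neuropsychological testing schedules the full battery at baseline and yearly. The nearest thing to a completeness rule is that "comparisons will take place when the full contingent of patients are accrued and have completed such assessments". That fixes when the analysis is run, not what happens to a patient who is never tested at 24 or 36 months. The six-month testing window does not settle this either.

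**The concern.** A classical repeated-measures ANOVA needs a complete row of scores, so one missed year removes a patient from the whole analysis, the 12-month information included. A paired t-test loses only patients without a score at its own time point. The two planned analyses of the same score can therefore rest on different patients.

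The harm comes if those who decline are the ones lost. The survivors then look better than the cohort, and there is no control arm to show it. The background sections give a reason to consider this: cognitive decline and dementia are said to matter because "development of these features leads to early disability and death", and of dementia the protocol says "It also is a strong predictor of survival". Neuropsychological scores are the primary efficacy parameters, so understated decline would favour the device.

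Separately, the HRQOL regression is meant to determine relationships. In 12 patients a high R² can arise from noise alone.

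**Working it through.** The documents give no dropout rate, SD, effect size or power figure, so there is no plan figure to reproduce. From the documents come n = 12 and tests at 0, 12, 24 and 36 months. Everything else is assumed. The unit is one baseline SD.

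**1. Patients left.** With annual loss a, the expected number with all tests is 12(1−a)³, and the chance that all 12 are complete is (1−a)³⁶.
- a = 5%: 12 × 0.95³ = 10.3; 0.95³⁶ = 16%.
- a = 15%: 12 × 0.85³ = 7.4; 0.85³⁶ = 0.3%.

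**2. Noise.** Assumed residual variance is 0.2 and slope SD 0.28 per year (intercept variance 0.8). The SD of 36-month change is √(2 × 0.2 + 9 × 0.28²) = 1.05, so the standard error at n = 12 is 1.05/√12 = 0.30.

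**3. Loss tied to the last observed decline.** This is a simulation with true change +0.20 at 12 months and −0.60 at 36. Loss is logistic in decline. First-year loss is random here, which by construction spares the 12-month t-test.

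| Annual loss | Log-odds per SD | 36-month mean, patients still tested | 12-month paired t-test | 12-month mean, complete cases |
|---|---|---|---|---|
| 5% | 0.5 | −0.57 | about +0.20 | +0.22 |
| 5% | 1 | −0.55 | about +0.20 | +0.24 |
| 5% | 2 | −0.51 | about +0.20 | +0.27 |
| 15% | 0.5 | −0.52 | about +0.20 | +0.26 |
| 15% | 1 | −0.45 | about +0.20 | +0.31 |
| 15% | 2 | −0.36 | about +0.20 | +0.38 |

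At log-odds 0.25 the 36-month means are −0.59 (5%) and −0.56 (15%). The 36-month bias is therefore 0.01 to 0.09 at 5% and 0.04 to 0.24 at 15%. Unrelated loss gives −0.60, so no bias.

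**4. Loss tied to the score not seen.** At log-odds 0.5, 1 and 2, patients still tested show −0.55, −0.50, −0.43 (5%) and −0.44, −0.31, −0.16 (15%) at 36 months. The 12-month paired t-test now moves too, to between +0.21 and +0.32.

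**5. The mixed model at 36 months** (categorical visit, unstructured covariance, Kenward-Roger; same log-odds).
- Observed-decline loss: −0.60, −0.59, −0.60 (5%) and −0.63, −0.61, −0.58 (15%). Coverage of the 95% interval is 95–96% and 92–93%.
- Unseen-score loss: −0.57, −0.53, −0.50 and −0.52, −0.40, −0.31. Bias is reduced, not removed.
- Random intercept only, observed-decline loss: −0.59 to −0.56 and −0.58 to −0.48, coverage 85–88%.

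**6. Overall accuracy (RMSE).** At 12 months the model had 0.20–0.24 against 0.22–0.33 for the complete-case ANOVA. At 36 months under observed-decline loss, model and paired t-test were level at 5% (about 0.33 each), with no consistent gain at 15%. With complete data the model returns the ANOVA's estimates.

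**7. HRQOL regression.** Expected R² from noise alone is k/(n−1): 2/11 = 0.18, 4/11 = 0.36, 6/11 = 0.55 for an assumed 2, 4 and 6 predictors. Simulated power at a true R² of 0.25 is 29%, 18% and 12%.

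**The case against.** The case for leaving this as a minor point is substantial.

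- **Loss may be low.** The statements on dementia and survival are general background. The Brain Bank Registry section regards a death on study as unlikely, patients with MMSE of 23 or below are excluded, patients unable to travel to the site are excluded, and the testing window is wide. This stands. The 15% figures are illustrations, not forecasts.
- **Complete-case deletion is inferred.** The plan neither states it nor specifies a 12-month contrast from the ANOVA. This stands. A reader might infer from the table that the plan's 12-month result will be inflated. The documents do not support that, because the planned 12-month comparison is the t-test.
- **The model buys little at 36 months.** This stands for overall accuracy when loss follows observed decline. In a harsher scenario with about 7.1 of 12 patients left, the t-test averaged −0.18 (SD 0.41) and the unstructured model −0.58 (SD 0.62), against a truth of −0.60. RMSE is √(0.42² + 0.41²) = 0.59 against √(0.02² + 0.62²) = 0.62, so bias is exchanged for variance.
- **Patients too impaired to test are the unseen-score case**, which the model only partly repairs, and a score after death has no clear meaning. This stands and shapes the fix.
- **The primary endpoint is a percentage change.** A model in score units does not check it directly. This stands.

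None of this defends the ANOVA itself. If complete rows are required it discards usable scores; the model gives the same estimates when nothing is missing and was more accurate at 12 months in every loss setting run.

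**Conclusion.** The point holds in a limited form. The available text makes no provision for missed tests, and a repeated-measures ANOVA run classically would be the weaker of two readily available methods. How much it matters rests on assumed loss rates and on an assumed link between loss and decline. At 5% annual loss tied to observed decline, the 36-month bias of 0.01 to 0.09 SD is small against a standard error of 0.30 SD. At 15% it reaches 0.24 SD in the strongest case run. With unrelated loss there is none.

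Two stronger conclusions do not follow. One is that the trial's results will be biased towards the device: the documents give no loss rate and no evidence of selective loss in this study. The other is that the mixed model should displace the primary t-tests or would validate them. It assumes that missingness depends only on observed data, and both analyses could agree and be wrong.

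The HRQOL point is secondary but firm for several predictors at n = 12. The battery list and evaluation table are missing from the text available, so the predictor counts are assumed and their absence is not held against the plan.

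**What to change.** **Longitudinal analysis.** Replace the repeated-measures ANOVA with a likelihood-based mixed model for each score, using all available tests at baseline, 12, 24 and 36 months. Visit stays categorical, as in the ANOVA. Specify REML, unstructured covariance, Kenward-Roger degrees of freedom, and a stated fallback (for example a random patient intercept if fewer than five patients have a 36-month test or the fit fails). Leave out years 4 and 5, where the Follow-Up section makes further evaluation depend on need.

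**Primary tests.** Keep the paired t-tests as primary. Report the model's 12- and 36-month contrasts beside paired t-tests of raw score change as a missing-data sensitivity analysis, and state that this does not directly check the percentage-change endpoint.

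**Missed tests.** Record a reason for each. Report deaths separately, without assigning scores. Repeat the analysis with missing scores of living patients lowered by 0.25 and 0.5 SD. With 14% or 39% missing at 36 months, all in living patients, that moves the mean by 0.14 × 0.25 = 0.04 and 0.14 × 0.5 = 0.07, or 0.39 × 0.25 = 0.10 and 0.39 × 0.5 = 0.19 (to rounding).

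**HRQOL regression.** Label it exploratory and limit it to one or two pre-named predictors with confidence intervals.

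**Cost.** SAP wording, standard software and one added data item. The fallback was needed in at most 0.1% of simulated trials at 5% loss and 4–6% at 15%; it keeps part of the bias and its intervals are too narrow. The 36-month interval stays wide (half-width about 0.7 to 0.8 SD). Multivariable prediction of HRQOL is largely given up, and even one observed correlation of 0.5 has a 95% interval of −0.10 to 0.83.

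### The regression on postsurgical HRQOL does not name presurgical HRQOL as a predictor, so a variable that only tracks starting quality of life can look like a predictor of outcome (minor point)

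*Combined protocol and SAP*

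**What the plan says.** The regression is described in one sentence, the last in Assessment and Statistical Analyses: "Hierarchical multiple regression analyses will be used to determine the relationship between presurgical psychosocial and neuropsychological variables and postsurgical outcome, as measured by HRQOL". The predictors are "presurgical psychosocial and neuropsychological variables" and the dependent variable is "postsurgical outcome, as measured by HRQOL". The sentence does not give the blocks, their order of entry, the HRQOL instrument, the time point or a significance level.

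Two nearby sentences bear on the point:

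- Change in HRQOL is handled by a different method: "Changes in cognitive functioning, mood, and HRQOL from presurgical baseline will be analyzed using repeated-measures ANOVAs". This implies that HRQOL is measured before surgery.
- Covariates are named for the analyses of covariance: "Demographic variables and measures of social support and locus of control will be entered into analyses of covariance whenever appropriate". Presurgical HRQOL is not among them.

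The design has one arm. Under Basic study plan, all twelve patients receive both electrodes. Neither Assessment and Statistical Analyses nor Statistical method/rationale lists HRQOL as a primary or secondary efficacy parameter.

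**The concern.** Quality of life before surgery will usually carry over, in part, to quality of life afterwards. Social support, locus of control and cognition may plausibly be related to it before surgery. A model that relates such variables to postsurgical HRQOL without the starting value therefore mixes two things: the variable's link to where the patient began, and any link to what followed.

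The first link alone can produce a significant coefficient, which a reader may take as a sign of how patients fare after tandem stimulation. The reverse can also happen. If a variable goes with poorer presurgical HRQOL but a better later course, the two links partly cancel and a real predictor can be missed. If they point the same way, the predictor looks stronger than it is.

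This is separate from the small sample. Omitting the baseline leaves the same spurious association at any sample size, and more patients only make it easier to detect.

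**Working it through.** **Inputs from the documents.** The sample is 12 patients in one group ("We propose a pilot study of tandem DBS in 12 PD patients"). The plan gives no significance level, effect size, standard deviation or correlation for this regression, so there is no stated figure to reproduce. Two-sided testing is stated only for the primary-endpoint t-tests ("Two-sided two-sample t-tests will compare post-operative changes to pre-operative data").

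**Assumptions.** Normal data, equal standard deviations before and after surgery, one predictor, two-sided 5%. B is presurgical HRQOL, P is postsurgical HRQOL and X is the presurgical variable.

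- r, the correlation of X with B: 0.3 to 0.6.
- s, the correlation of B with P: 0.5 to 0.8.
- X has no relation to P once B is held fixed.

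**Step 1: the association induced by leaving out B.** Under these assumptions corr(X, P) = r × s. At 0.5 and 0.7 this is 0.5 × 0.7 = 0.35. Across the range it runs from 0.3 × 0.5 = 0.15 to 0.6 × 0.8 = 0.48. With 12 patients a sample correlation is significant beyond ±0.576.

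**Step 2: how often X is declared significant** (simulation, 100,000 trials per setting):

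| r | s | r × s | Without B | With B as first block |
|---|---|---|---|---|
| 0.3 | 0.5 | 0.15 | about 8% | about 5% |
| 0.3 | 0.7 | 0.21 | 9.9% | about 5% |
| 0.5 | 0.5 | 0.25 | 12.3% | about 5% |
| 0.5 | 0.7 | 0.35 | about 20% | about 5% |
| 0.6 | 0.8 | 0.48 | about 37% | about 5% |

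At r = 0.5 and s = 0.7 the rate without B rises to about 40% with 24 patients and 72% with 50.

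**Step 3: a change score instead of P.** If the outcome is P − B and B is not in the model, X is still linked to B, in the opposite direction. At r = 0.5 and s = 0.7 the rate is 9.0%. Over a slightly wider grid (r 0.3 to 0.7, s 0.5 to 0.85) it is 5.8% to 20.1%.

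**Step 4: a variable that does predict.** Let P = 0.7B + error + 0.7X, where the error has variance 1 − 0.7² = 0.51.

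- r = −0.5: cov(X, P) = 0.7 − 0.35 = 0.35 and var(P) = 1 + 0.49 − 0.49 = 1, so corr(X, P) = 0.35. Power is about 20% without B and 63% with B.
- r = +0.5: cov(X, P) = 0.7 + 0.35 = 1.05 and var(P) = 1 + 0.49 + 0.49 = 1.98, so corr(X, P) = 1.05/√1.98 = 0.75. Power is about 86% without B and 63% with B. Part of the 86% is the baseline link.

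The 0.7 on B is a coefficient here. In the r = −0.5 case the pre-to-post HRQOL correlation is itself only 0.7 − 0.35 = 0.35.

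**Step 5: error in measuring B.** Suppose X and P relate to true presurgical HRQOL, and the observed correlations are still 0.5 and 0.7. The rate with B in the model is then about 7% if the baseline measure has reliability 0.8, and about 11% at 0.7. Both reliabilities are assumed.

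**The case against.** The strongest reply is that the gap is read from one short sentence. It does not say whether outcome means the postsurgical level or a change, and a hierarchical model is entered in blocks, so a first block holding presurgical HRQOL would be compatible with it. That is fair, and the accurate statement is that presurgical HRQOL is not named, not that it is ruled out. The reply does not remove the point. No section names such a block, the change analysis is assigned to a different method, and step 3 shows that an unadjusted change score would need the same remedy.

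A second reply is that describing where patients end up is a legitimate aim, and an unadjusted model answers it. This also stands. A reader might infer that the plan tests the wrong hypothesis about who benefits from surgery, but the documents never state that aim; they speak only of a relationship with postsurgical outcome. Under the descriptive aim, the rejections in step 2 reflect a true correlation with later HRQOL. They mislead only if read as prediction beyond the starting value.

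A third reply is that adjustment does not deliver what a reader may want from it. In a single-arm study a variable that predicts the natural course of HRQOL stays significant after adjustment, and step 5 shows that measurement error can leave some bias. Both are correct and limit what the fix can claim.

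Finally, the regression is peripheral in a 12-patient pilot. That bears on the weight of the point, not on whether it is right.

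**Conclusion.** The point holds as a minor one. On the plain reading, presurgical HRQOL is missing from the named predictors, and a variable related only to starting HRQOL is declared significant about 8% to 37% of the time under the assumed correlations, against about 5% with the baseline included. These figures are illustrative: they rest on one predictor, 12 patients, normal data, a 5% level and correlations that the documents do not give.

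Three stronger readings are not supported:

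- That the error rate is at least doubled in all but the weakest setting. It is 9.9% at 0.3 and 0.7, about 8.7% at 0.3 and 0.6, and about 9.6% at 0.4 and 0.5.
- That the omission always hides real predictors. It hides or inflates them, depending on the sign of their correlation with presurgical HRQOL.
- That adjustment would show who benefits from surgery. With one arm it shows only prediction of HRQOL beyond the starting value.

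The analysis is neither primary nor a listed secondary, so the trial's main conclusions do not depend on it.

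**What to change.** Replace the regression sentence in Assessment and Statistical Analyses with wording such as: *Postsurgical HRQOL will be regressed on presurgical HRQOL (step 1) and then on the presurgical variable of interest (step 2). The test of interest is the contribution added at step 2. The analysis is exploratory.* State the HRQOL instrument, the postsurgical time point and the order of entry in the same place. Add that the result describes prediction of HRQOL beyond the starting value and does not separate response to surgery from natural course.

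The cost is a few sentences and one residual degree of freedom: with 12 patients and one predictor, 12 − 2 = 10 becomes 12 − 3 = 9. Some apparent predictors may no longer be significant. No new data are needed if HRQOL is collected before surgery, as the planned change analysis implies. The contents of the evaluation table are not in the text available for review, so the sponsor should confirm this.
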